10.2 Demographics and Subject Disposition

The demographic variables age, sex, race, ethnicity, body weight, height, and body mass index will be summarized for each part and listed. Subject disposition will be summarized for each part and listed.

10.3 Pharmacokinetic Assessment

10.3.1 Pharmacokinetic Analysis

Pharmacokinetic parameters will be determined from plasma concentrations of LOXO-292 and [¹⁴C]-LOXO-292 and whole blood and plasma concentrations of total radioactivity using a

model-independent approach performed using Phoenix WinNonlin (Certara USA, Inc.) version 6.4 or higher. Pharmacokinetic parameters for relevant metabolites of LOXO-292 may be calculated in Part 1 by the Radioanalysis Department or Metabolite Profiling Lab and reported in those phase sub-reports, as deemed appropriate. In Parts 1 and 2, additional PK parameters may be determined where appropriate.

Pharmacokinetic analysis will, where possible, be carried out using actual postdose times recorded on the eCRF. If actual times are missing, nominal times may be used with Sponsor approval.

Concentrations are used as supplied by the analytical laboratory for PK analysis. The units of concentration and resulting PK parameters, with amount or concentration in the unit, will be presented as they are received from the analytical laboratory.

Part 1

The following PK parameters will be determined for each subject, where possible, from the plasma concentrations of LOXO-292 and whole blood and plasma concentrations of total radioactivity:

Parameter	Definition
C_{\max}	Maximum observed concentration
T_{\max}	Time to maximum observed concentration
AUC_{last}	AUC from time 0 to the time of the last quantifiable concentration, calculated using the linear trapezoidal rule for increasing and decreasing concentrations
$AUC_{0-\infty}$	AUC extrapolated to infinity, calculated using the formula: $AUC_{0-\infty} = AUC_{\text{last}} + (C_{\text{last}} \div \lambda_z)$ where C_{last} is the last quantifiable concentration and λ_z is the apparent terminal elimination rate constant
$\%AUC_{\text{extrap}}$	percentage of AUC that is due to extrapolation from the last quantifiable concentration to infinity
λ_z	Apparent terminal elimination rate constant, where λ_z is the magnitude of the slope of the linear regression of the log concentration versus-time profile during the terminal phase
$t_{1/2}$	Apparent terminal elimination half-life (whenever possible), where $t_{1/2} = \text{natural log (2)} / \lambda_z$
CL/F	Apparent systemic clearance (for LOXO-292 only)

V _z /F	Apparent volume of distribution during the terminal elimination phase (for LOXO-292 only)
Blood/Plasma AUC Ratio	AUC _{0-∞} of total radioactivity in whole blood / AUC _{0-∞} of total radioactivity in plasma
Plasma LOXO-292 / Total Radioactivity AUC Ratio	AUC _{0-∞} of LOXO-292 in plasma / AUC _{0-∞} of total radioactivity in plasma.

The AUC ratios (AUC total radioactivity in whole blood to AUC total radioactivity in plasma, and AUC of Plasma LOXO-292 to AUC of plasma total radioactivity) will be based on AUC_{0-∞}. Where AUC_{0-∞} cannot be reliably calculated, an alternative AUC measure, such as AUC_{last} or AUC to a common timepoint, may be used.

Additionally, blood-to-plasma concentration ratios at each sampling timepoint will be calculated (by the Covance Radioanalysis Department) and reported in the radioanalysis report to determine partitioning of total radioactivity into red blood cells.

In addition, for each subject, the following PK parameters will be calculated whenever possible, based on the urine concentrations of total radioactivity:

Parameter	Definition
A _{eu}	amount excreted in urine per sampling interval
Cum A _{eu}	cumulative amount excreted in urine
%f _{eu}	percentage of dose excreted in urine per sampling interval, where %f _{eu} = 100 (A _{eu} /dose)
Cum %f _{eu}	cumulative percentage of dose excreted in urine.

For each subject, the following PK parameters will be calculated whenever possible, based on the fecal concentrations of total radioactivity:

Parameter	Definition
A _{ef}	amount excreted in feces per sampling interval
Cum A _{ef}	cumulative amount excreted in feces
%f _{ef}	percentage of dose excreted in feces per sampling interval, where %f _{ef} = 100 (A _{ef} /dose)
Cum %f _{ef}	cumulative percentage of dose excreted in feces

All PK parameters for total radioactivity in urine and feces will be calculated by the Covance Radioanalysis Department and will be reported in the radioanalysis report. The Covance Radioanalysis Department will also calculate and report the amount of total radioactivity in total excreta (feces + urine).

The amount excreted in urine or feces (A_{eu} or A_{ef}) for each collection interval will be calculated as the product of concentration and sample weight; Cum A_{eu} and Cum A_{ef} will be calculated by summing the A_{eu} or A_{ef} values for each collection interval.

The percentage of the dose excreted in urine or feces (% f_{eu} or % f_{ef}) will be calculated for each collection interval (i) and cumulatively according to the following formula:

$$\%f_e(i) = \frac{A_e(i)}{\text{dose}} \times 100$$

Part 2

Oral Dose PK: the following PK parameters will be calculated for each subject, where possible, based on the plasma concentrations of LOXO-292:

Parameter	Definition
C_{max}	Maximum observed concentration
T_{max}	Time to maximum observed concentration
AUC_{last}	AUC from time 0 to the time of the last quantifiable concentration, calculated as described for Part 1
$AUC_{0-\infty}$	AUC extrapolated to infinity, calculated as described for Part 1
% AUC_{extrap}	percentage of AUC that is due to extrapolation from the last quantifiable concentration to infinity
λ_z	Apparent terminal elimination rate constant
$t_{1/2}$	Apparent terminal elimination half-life (whenever possible), calculated as described for Part 1
F	Absolute bioavailability, calculated as
	$F = \frac{AUC_{0-\infty}(\text{oral}) \times \text{Dose (IV)}}{AUC_{0-\infty}(\text{IV}) \times \text{Dose (oral)}}$
CL/F	Apparent systemic clearance
V_z/F	Apparent volume of distribution during the terminal elimination phase

IV dose PK: the following PK parameters will be calculated for each subject, where possible, based on the plasma concentrations of [¹⁴C]-LOXO-292:

Parameter	Definition
C_{max}	Maximum observed concentration
T_{max}	Time to maximum observed concentration
AUC_{last}	AUC from time 0 to the time of the last quantifiable concentration, calculated as described for Part 1

$AUC_{0-\infty}$	AUC extrapolated to infinity, calculated as described for Part 1
$\%AUC_{\text{extrap}}$	percentage of AUC that is due to extrapolation from the last quantifiable concentration to infinity
λ_z	Apparent terminal elimination rate constant
$t_{1/2}$	Apparent terminal elimination half-life (whenever possible), calculated as described for Part 1
CL	Systemic clearance
V_{ss}	Volume of distribution at steady state
V_z	Volume of distribution during the terminal phase

In addition, for each subject, the following PK parameters will be calculated, whenever possible, based on the urine concentrations of LOXO-292, [^{14}C]-LOXO-292, and total radioactivity:

Parameter	Definition
A_{eu}	amount excreted in urine per sampling interval
Cum A_{eu}	cumulative amount excreted in urine
CL_R	renal clearance (LOXO-292 and [^{14}C]-LOXO-292 only), where $CL_R = \text{Cum } A_{eu}/AUC_{0-\infty}$ or AUC over a common timepoint between urine and plasma sample $AUC_{0-\infty}$ may be used, if appropriate
$\%f_{eu}$	cumulative percentage of dose excreted in urine
Cum $\%f_{eu}$	cumulative percentage of dose excreted in urine

For each subject, the following PK parameters will be calculated, whenever possible, based on the fecal concentrations of total radioactivity:

Parameter	Definition
A_{ef}	amount excreted in feces per sampling interval
Cum A_{ef}	cumulative amount excreted in feces
$\%f_{ef}$	percentage of dose excreted in feces per sampling interval, where $\%f_{ef} = 100 (A_{ef}/\text{dose})$
Cum $\%f_{ef}$	cumulative percentage of dose excreted in feces

The following excretion parameters will be calculated, whenever possible, based on total radioactivity in total (urine+feces) excreta:

Parameter	Definition
%f _e	percentage of dose excreted in urine and feces per sampling interval, where $\%f_e = \%f_{eu} + \%f_{ef}$
Cum %f _e	cumulative percentage of dose excreted in urine and feces, calculated as the sum of the percentage of dose excreted in urine and feces for each collection period

C_{max} and T_{max} will be obtained directly from the plasma and whole blood concentration-time profiles.

For multiple peaks, the highest postdose concentration will be reported as C_{max}. In the case that multiple peaks are of equal magnitude, the earliest T_{max} will be reported.

The amount excreted (A_e) in urine and feces for each collection interval will be calculated as the product of analyte concentration in urine or feces and sample weight. Cumulative A_e will be calculated by summing the A_e values for each collection interval over the sampling period.

10.3.2 Criteria for Handling Concentrations Below the Limit of Quantification in Pharmacokinetic Analysis

Concentration values that are below the limit of quantification (BLQ) will be set to zero, with defined exceptions as follows;

- Any embedded BLQ value (between 2 quantifiable concentrations) and BLQ values following the last quantifiable concentration in a profile will be set to missing for the purposes of PK analysis.
- If there are late positive concentration values following 2 BLQ concentration values in the apparent terminal phase, these values will be evaluated. If these values are considered to be anomalous, they will be set to missing.
- If an entire concentration-time profile is BLQ, the profile will be excluded from the PK analysis.
- If a predose concentration is missing, these values may be set to zero with Sponsor approval

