### **7.3 Pharmacokinetic Analysis**

#### **Part 1:**

Whenever possible, the following PK parameters will be calculated for each subject, based on the plasma concentrations of LOXO-292 and the whole blood and plasma concentrations of total radioactivity, according to the model independent approach.

$C_{\max}$	maximum observed concentration
$T_{\max}$	time to maximum observed concentration
$AUC_{\text{last}}$	AUC from time 0 to the time of the last quantifiable concentration, calculated using the linear trapezoidal rule for increasing concentrations and the logarithmic rule for decreasing concentrations
$AUC_{0-\infty}$	AUC extrapolated to infinity, calculated using the formula: $AUC_{0-\infty} = AUC_{\text{last}} + (C_{\text{last}} \div \lambda_z)$

$\lambda_z$	where $C_{last}$ is the last quantifiable concentration and $\lambda_z$ is the apparent terminal elimination rate constant
$t_{1/2}$	apparent terminal elimination rate constant, where $\lambda_z = \ln 2 / t_{1/2}$
CL/F	where $t_{1/2} = \ln 2 / \lambda_z$
V z /F	apparent systemic clearance (for LOXO-292 only)
	apparent volume of distribution during the terminal phase (for LOXO-292 only)

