**Plasma LOXO-292 /Total Radioactivity AUC Ratio**

$AUC_{0-\infty}$  of LOXO-292 in plasma/ $AUC_{0-\infty}$  of total radioactivity in plasma.

Additionally, blood-to-plasma ratios at each sampling timepoint will be calculated to determine partitioning of total radioactivity into red blood cells.

In addition, for each subject, the following PK parameters will be calculated whenever possible, based on the urine concentrations of total radioactivity:

A eu	amount excreted in urine per sampling interval
Cum A eu	cumulative amount excreted in urine
%f eu	percentage of dose excreted in urine per sampling interval, where $\%f_{eu} = 100 (A_{eu}/dose)$
Cum %f eu	cumulative percentage of dose excreted in urine.

For each subject, the following PK parameters will be calculated whenever possible, based on the fecal concentrations of total radioactivity:

A ef	amount excreted in feces per sampling interval
Cum A ef	cumulative amount excreted in feces
%f ef	percentage of dose excreted in feces per sampling interval, where $\%f_{ef} = 100 (A_{ef}/dose)$
Cum %f ef	cumulative percentage of dose excreted in feces.

Part 2:

Oral dose PK: Whenever possible, the following PK parameters will be calculated for each subject, based on the plasma concentrations of LOXO-292:

$C_{max}$	maximum observed concentration
$T_{max}$	time to maximum observed concentration
$AUC_{last}$	AUC from time 0 to the time of the last quantifiable concentration
$AUC_{0-\infty}$	AUC extrapolated to infinity, calculated as described above
$\lambda_z$	apparent terminal elimination rate constant
$t_{1/2}$	apparent terminal elimination half-life (whenever possible), where $t_{1/2} = \text{natural log (2)}/\lambda_z$
F	absolute bioavailability, calculated using the formula: $F = \frac{AUC_{0-\infty}(\text{oral}) \times \text{Dose (IV)}}{AUC_{0-\infty}(\text{IV}) \times \text{Dose (oral)}}$
CL/F	apparent systemic clearance
$V_z/F$	apparent volume of distribution during the terminal phase.

Intravenous dose PK: For each subject, the following PK parameters will be calculated whenever possible, based on the plasma concentrations of [C]-LOXO-292:

$C_{max}$	maximum observed concentration
$T_{max}$	time to maximum observed concentration
$AUC_{last}$	AUC from time 0 to the time of the last quantifiable concentration
$AUC_{0-\infty}$	AUC extrapolated to infinity, calculated as described above

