4 INTRODUCTION

This SAP has been developed after review of the clinical study protocol (Final Version dated 15 June 2018, Protocol Amendment 1 dated 12 July 2018, and Protocol Amendment 2 dated 15 August 2018).

This SAP describes the planned analysis of the safety, tolerability, and PK data from this study. A detailed description of the planned TFLs to be presented in the Clinical Study Report (CSR) is provided in the accompanying TFL shell document.

The intent of this document is to provide guidance for the statistical analyses of safety and PK data. In general, the analyses are based on information from the protocol, unless they have been modified by agreement between Loxo Oncology, Inc. and Covance Early Clinical Biometrics. A limited amount of information concerning this study (e.g., objectives, study design) is given to help the reader's interpretation. This SAP must be finalized prior to the lock of the clinical database for this study. When the SAP and TFL shells are agreed upon and finalized, they will serve as the template for this study's CSR.

This SAP supersedes the statistical considerations identified in the protocol; where considerations are substantially different, they will be so identified. If additional analyses are required to supplement the planned analyses described in this SAP, they may be performed and will be identified in the CSR. Any substantial deviations from this SAP will be agreed upon between Loxo Oncology, Inc. and Covance Early Clinical Biometrics and identified in the CSR.

This SAP is written with consideration of the recommendations outlined in the International Council for Harmonisation (ICH) E9 guideline entitled, "Guidance for Industry: Statistical Principles for Clinical Trials" and the ICH E3 guideline entitled, "Guidance for Industry: Structure and Content of Clinical Study Reports."^{1,2}

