12 CHANGES FROM THE PROTOCOL SPECIFIED STATISTICAL ANALYSES

There were no changes from the protocol-specified statistical analyses.

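### The SAP integrates falling concentrations linearly where the protocol specifies the logarithmic rule, and declares no change; AUC is biased upward and clearance downward

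*SAP*

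**What the plan says.** - **Protocol 7.3, Part 1:** AUClast is "calculated using the linear trapezoidal rule for increasing concentrations and the logarithmic rule for decreasing concentrations". AUC0-∞ adds the last quantifiable concentration divided by λz.
- **Protocol 7.3, Part 2:** the oral and IV AUC0-∞ entries refer back to that definition ("AUC extrapolated to infinity, calculated as described above"). The Part 2 AUClast entries name no rule.
- **SAP 10.3.1, Part 1:** AUClast is "calculated using the linear trapezoidal rule for increasing and decreasing concentrations".
- **SAP 10.3.1, Part 2:** the oral and IV tables import the Part 1 rule for both parameters: "AUC from time 0 to the time of the last quantifiable concentration, calculated as described for Part 1" and "AUC extrapolated to infinity, calculated as described for Part 1". F is the dose-normalised ratio of oral to IV AUC0-∞.
- **SAP 10.3.4**, which deals with AUC calculation, gives no other integration rule.
- **SAP 4:** "This SAP supersedes the statistical considerations identified in the protocol; where considerations are substantially different, they will be so identified".
- **SAP 12:** "There were no changes from the protocol-specified statistical analyses".

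**The concern.** Both definitions are legible and current, and they cannot both be followed. Because the SAP takes precedence, and Protocol 7.6 has the outputs programmed from the final SAP, the linear rule is the one that would be run. The SAP is also to serve as the template for the study report, so its no-change statement could carry over into that report.

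The choice is not neutral. On an exponentially falling curve the straight line between two samples lies above the curve, so the linear rule always overstates the area. An IV push over about 2 minutes falls over nearly its whole profile, and late samples are usually widely spaced.

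AUC0-∞ feeds F (the first-listed primary objective of Part 2), CL, CL/F, Vz, Vz/F, Vss and both Part 1 AUC ratios. It can also feed CLR. It is the denominator of the extrapolated percentage that SAP 10.3.4 uses to flag values from 20% and to exclude them from descriptive statistics above 30%. The extrapolated piece itself does not depend on the rule, so a larger total makes that screen slightly more lenient.

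**Working it through.** The plan states no figure that depends on the AUC rule, so there is nothing to reproduce. The check sizes the difference between the two rules.

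**Inputs from the documents**
- The two AUC rules: Protocol 7.3 and SAP 10.3.1.
- Half-life at least 12 h: Protocol 2.3.
- Part 2 sampling to 192 h: Protocol 4.1 and SAP 6.2.
- At most 25 PK blood samples per part: Protocol Appendix B.
- Individual draw times: redacted.

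**Step 1: one falling interval, mono-exponential decline.** With x = ln 2 × (interval ÷ half-life), linear area ÷ true area = (x/2)(1 + e^−x)/(1 − e^−x). The logarithmic rule is exact here.
- Interval of one half-life: 0.3466 × 1.5/0.5 = 1.040, an overstatement of 4.0%.
- Interval of two half-lives: 0.6931 × 1.25/0.75 = 1.155, an overstatement of 15.5%.
- The same formula gives 1.0% at half a half-life and 33.7% at three.

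With a 12 h half-life, a 24 h gap between samples is the two-half-life case. These are errors in single intervals, not in a reported parameter.

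**Step 2: whole profiles.** Oral and IV curves, with the IV dose at 2 h, were integrated by each rule, with AUC0-∞ = AUClast + Clast/λz. Assumptions:
- terminal half-life 12, 24 or 32 h;
- absorption rate 1.2 per hour;
- fast-phase share of the initial IV concentration 0, 0.7 (half-life 1.0 h) or 0.9 (half-life 0.5 h);
- a 25-sample grid to 122 h or a 20-sample grid to 192 h;
- noise-free data and a known initial IV concentration.

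Selected results, in percent, each cell oral / IV unless marked:

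| Grid | Half-life (h) | Fast share | Linear vs truth | Log-down vs truth | Linear vs log-down (oral / IV / F) |
|---|---|---|---|---|---|
| 25 | 12 | 0 | +2.5 / +2.8 | −0.1 / 0.0 | +2.6 / +2.8 / −0.2 |
| 25 | 32 | 0.7 | +0.8 / +1.0 | 0.0 / +0.1 | +0.8 / +0.9 / −0.1 |
| 25 | 32 | 0.9 | +0.6 / +1.3 | −0.2 / +0.3 | +0.8 / +1.0 / −0.2 |
| 20 | 24 | 0.7 | +1.9 / +2.6 | −0.2 / +0.4 | +2.1 / +2.3 / −0.2 |
| 20 | 12 | 0 | +4.9 / +5.5 | −0.3 / 0.0 | +5.2 / +5.5 / −0.3 |
| 20 | 12 | 0.9 | +3.0 / +6.0 | −1.1 / +1.1 | +4.1 / +4.8 / −0.7 |

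Over all 18 combinations, linear overstates AUC0-∞ by 0.6% to 6.0% (oral and IV together), while linear-up/log-down stays within −1.1% to +1.1%.

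**Step 3: derived parameters.**
- CL = dose ÷ AUC0-∞. An IV AUC higher by 0.9% to 5.5% gives CL lower by 1 − 1/1.009 = 0.9% to 1 − 1/1.055 = 5.2%.
- CL/F is lower by 1 − 1/1.008 = 0.8% to 1 − 1/1.052 = 4.9%.
- Vz and Vz/F equal these clearances divided by λz, which the rule does not touch, so they shift by the same percentages.
- F changes by the ratio of the two shifts. In the last row this is 1.041/1.048 − 1 = −0.7%, the largest change found.

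**Step 4: sensitivity to the assumptions.** Other assumed grids (16 to 25 samples), half-lives up to 36 h and distribution half-lives of 0.3 to 2 h give the same picture. Taken together with the runs above, the linear rule overstates IV AUC0-∞ by 0.8% to 6.0% and oral by 0.4% to 4.9%. Linear-up/log-down stays within −1.1% to +1.7%. F differs between the rules by about 1% relative at most; with a true F of 0.70, one set gave 0.685–0.699 (linear) and 0.688–0.699 (log-down).

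**The case against.** The strongest reply is that the conflict is real but has little consequence. F barely moves, because oral and IV AUCs are biased in the same direction. This stands: the argument for correction rests on AUC, clearance and volume and on the inaccurate declaration, not on a materially wrong F.

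The size also depends on draw times that cannot be seen. With 25-sample grids, matching the maximum in Appendix B, the IV overstatement was 0.8% to 4.6%, and at most 2.7% for half-lives of 24 to 36 h. A 5% shift in CL is therefore near the upper end. This stands too, though no plausible grid reverses the direction.

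Further limits are fair. The protocol's Part 2 AUClast entries name no rule, so the conflict is explicit there only for AUC0-∞. SAP 10.3.1 lets CLR use AUC to a common timepoint. The Part 1 AUC ratios should partly cancel. Mass balance, recovery, Cmax, Tmax, λz and half-life are unaffected. Log-down can slightly underestimate around a rounded oral peak.

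It can also be argued that a low single-digit shift in a descriptive study of 6 subjects per part is not substantial in the sense of SAP Section 4, and that Protocol 7.3 leaves data handling to the SAP. Neither point makes the statement in Section 12 accurate. Delegating further detail is not the same as reversing a method the protocol states, and Protocol 7.4 expects deviations from the original plan to be reported. A consistently applied linear rule is workable, but it has to be declared.

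**Conclusion.** The concern holds, and the SAP is wrong as written. The contradiction and the inaccurate no-change statement follow from the text and need no assumptions. The direction of the bias follows from mathematics for exponentially falling concentrations.

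The size is conditional on assumed draw times and noise-free profiles: roughly 1% to 5.5% on AUC0-∞, and about 1% to 5% on CL, CL/F, Vz and Vz/F. The effect on F is about 1% relative or less. Shifts in Vss, CLR, the Part 1 AUC ratios and the extrapolated percentage were not computed.

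**What to change.** In SAP 10.3.1, replace the AUClast wording in the Part 1 table with the protocol's linear-up/log-down rule and state that it applies to all analytes and matrices for which AUC is calculated, in both parts. The Part 2 entries then inherit it through their existing cross-references, and Section 12 becomes accurate on this point.

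If the linear rule was intended, list it in Section 12 as a change from the protocol with a reason, and report AUC and F by linear-up/log-down as a sensitivity analysis.

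The first option costs one line of SAP text and one software setting before database lock. The second adds one entry in Section 12 and a repeat run of the noncompartmental analysis. Neither requires new data.

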3 ABBREVIATIONS

Abbreviations pertain to the SAP only (not the TFLs).

ADaM	Analysis Data Model
AE	adverse event
A_{ef}	amount excreted in feces per sampling interval
A_{eu}	amount excreted in urine per sampling interval
AME	absorption, metabolism, and excretion
AUC	area under the concentration-time curve
$AUC_{0-\infty}$	area under the concentration-time curve extrapolated to infinity
AUC_{last}	area under the concentration-time curve from time 0 to the time of the last quantifiable concentration
%AUC _{extrap}	percentage of AUC that is due to extrapolation from the last measurable concentration to infinity
Blood/Plasma AUC Ratio	$AUC_{0-\infty}$ of total radioactivity in whole blood/ $AUC_{0-\infty}$ of total radioactivity in plasma
BLQ	below the limit of quantitation
CDISC	Clinical Data Interchange Standards Consortium
CI	confidence interval
CL	systemic clearance
C_{last}	last quantifiable concentration
CL/F	apparent systemic clearance
CL _R	renal clearance
C_{max}	maximum observed concentration
CRU	Clinical Research Unit
CSR	Clinical Study Report
CTCAE	Common Terminology Criteria for Adverse Events
Cum A_{ef}	cumulative amount excreted in feces
Cum A_{eu}	cumulative amount excreted in urine
Cum %f _e	cumulative percentage of dose excreted in urine and feces
Cum %f _{ef}	cumulative percentage of dose excreted in feces
Cum %f _{eu}	cumulative percentage of dose excreted in urine
CV%	coefficient of variation

ECG	electrocardiogram
F	absolute bioavailability
%f _e	percentage of dose excreted in urine and feces per sampling interval
%f _{ef}	percentage of dose excreted in feces per sampling interval
%f _{eu}	percentage of dose excreted in urine per sampling interval
ICF	Informed Consent Form
ICH	International Council for Harmonisation / International Conference on Harmonisation
IV	intravenous
λ_z	apparent terminal elimination rate constant
LLOQ	lower limit of quantification
log	logarithm (base e)
Max	maximum
MetID	metabolite profiling and identification
Min	minimum
N	number of subjects
n	number of observations
NC	not calculated
NR	no result
PK	pharmacokinetic(s)
Plasma LOXO-292/ Total Radioactivity AUC Ratio	AUC _{0-∞} of LOXO-292 in plasma/AUC _{0-∞} of total radioactivity in plasma
QTc	QT correction; QT interval corrected for heart rate
QTcF	QT interval corrected for heart rate using Fridericia's method
R ²	adjusted coefficient for determination of exponential fit
RET	rearranged during transfection
SAP	statistical analysis plan

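### The SAP's Part 2 urine table defines %feu as cumulative, contradicting its own per-interval definition elsewhere and the per-interval %fe formula that uses it

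*SAP*

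**What the plan says.** SAP section 10.3.1 lists the Part 2 urine parameters for LOXO-292, [14C]-LOXO-292 and total radioactivity. It defines %feu as "cumulative percentage of dose excreted in urine" and gives no formula. The next row, Cum %feu, has the same definition.

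The other Part 2 rows are worded differently:

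- %fef is "percentage of dose excreted in feces per sampling interval, where" %fef = 100 (Aef/dose).
- %fe is "percentage of dose excreted in urine and feces per sampling interval, where" %fe = %feu + %fef.
- Cum %fe is the cumulative percentage in urine and feces, "calculated as the sum of the percentage of dose excreted in urine and feces for each collection period".

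Everywhere else %feu is an interval quantity:

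- The SAP abbreviation list (section 3), which is not limited to Part 1, has "percentage of dose excreted in urine per sampling interval".
- The SAP Part 1 urine table has "percentage of dose excreted in urine per sampling interval, where" %feu = 100 (Aeu/dose).
- Protocol section 7.3 gives the same definition and formula in its Part 2 urine list.

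SAP section 4 says that the SAP supersedes the protocol's statistical considerations and that substantial differences will be identified. SAP section 12 reports no changes.

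**The concern.** Within the Part 2 urine table, two symbols share one definition, and the symbol meant for the interval percentage carries the cumulative one. That would be untidy but harmless if nothing else used %feu. However, the %fe row uses it by name, in a sum that is itself labelled per interval and whose other term is per interval. A programmer who takes the row at face value would add cumulative urine to interval feces.

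The resulting %fe would not fall toward zero as excretion ends. It would settle near the total urinary share, so late collections would look like continuing excretion. The per-interval urinary percentages that the protocol lists for the three Part 2 analytes could also be reported as cumulative figures.

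**Working it through.** **The definitions compared.** No plan figure needs reproducing, because the point rests on wording.

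| Place | %feu is | Formula given |
|---|---|---|
| SAP section 3, abbreviations | per interval | none |
| SAP 10.3.1, Part 1 urine table | per interval | 100 (Aeu/dose) |
| Protocol 7.3, Part 2 urine list | per interval | 100 (Aeu/dose) |
| SAP 10.3.1, Part 2 urine table | cumulative | none |

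**Whether nearby text repairs the row.** The general SAP formula, which applies to each interval "and cumulatively according to the following formula", stands before the Part 2 heading. Part 2 refers back to Part 1 for AUC and half-life but not for %feu. The closing Part 2 paragraph, "in urine and feces for each collection interval will be calculated as the product of analyte concentration in urine or feces and sample weight", concerns amounts, not percentages. None of this changes the row.

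**Size of the error if the row is applied literally.** Let u_i and f_i be the percentages of dose in urine and feces in interval i.

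- Intended: %fe(i) = u_i + f_i
- Literal: %fe(i) = (u_1 + ... + u_i) + f_i
- Excess: u_1 + ... + u_(i-1), which is Cum %feu through interval i-1

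This is exact and needs no assumption. The excess is 0 in the first interval. In the last, it is total urine minus the last interval's urine.

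**Worked example with invented values.**

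| Interval | 1 | 2 | 3 | 4 | 5 | 6 | 7 | 8 | Sum |
|---|---|---|---|---|---|---|---|---|---|
| Urine | 6 | 5 | 4 | 3 | 2 | 2 | 1 | 1 | 24 |
| Feces | 3 | 12 | 15 | 14 | 8 | 5 | 3 | 1 | 61 |
| Intended %fe | 9 | 17 | 19 | 17 | 10 | 7 | 4 | 2 | 85 |
| Literal %fe | 9 | 23 | 30 | 32 | 28 | 27 | 26 | 25 | 200 |
| Excess | 0 | 6 | 11 | 15 | 18 | 20 | 22 | 23 | 115 |

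**Illustrative range.** The documents give sampling through 192 hours (protocol section 4.1). The collection intervals are redacted and no urinary share is stated. Assumptions:

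- Eight 24-hour intervals.
- Urinary share U of 5%, 10% or 20% of dose at 192 hours.
- Urinary half-life h of 12 to 72 hours. The low end echoes the plasma half-life of at least 12 hours in protocol section 2.3. The high end is a free choice.

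Cumulative urine is C(t) = U × (1 − 2^(−t/h)) / (1 − 2^(−192/h)).

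- Last interval, excess = C(168). At h = 72: U × 0.8016/0.8425 = 0.951 U. At h = 12: 1.000 U.
- Second interval, excess = C(24). At h = 72: U × 0.2063/0.8425 = 0.245 U. At h = 12: 0.750 U.

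| U | Second-interval excess | Last-interval excess | True urine in last interval |
|---|---|---|---|
| 5% | 1.2 to 3.8 | 4.8 to 5.0 | 0.0 to 0.2 |
| 10% | 2.4 to 7.5 | 9.5 to 10.0 | 0.0 to 0.5 |
| 20% | 4.9 to 15.0 | 19.0 to 20.0 | 0.0 to 1.0 |

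Splitting the first day into shorter collections leaves the last-interval figures unchanged, because that interval is still 168 to 192 hours.

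**The case against.** The best answer is that no careful analyst would be misled. The abbreviation list defines %feu per interval for the whole SAP. The %fe row says its result is per interval, which a cumulative term contradicts. Listing both %feu and Cum %feu makes no sense if they are the same quantity. Aeu and Cum Aeu are correctly separated just above. The protocol supplies the intended formula. All of this stands, and it makes a copying slip from the Cum %feu row much the likeliest explanation.

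It also rules out a stronger reading. From the Part 2 table alone, a reader might infer that the SAP has dropped the per-interval urinary percentage altogether. The abbreviation list defines it, so the supportable charge is an internal contradiction. Nor is there support for reading the row as a deliberate change, since SAP section 12 declares none.

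The magnitudes are also fairly challenged. They apply only under the literal reading, with assumed intervals, urinary shares and half-lives. Damage to the table when the PDF was made or converted cannot be excluded either, so the row should be checked against the signed SAP.

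What the objection does not remove is that the SAP supersedes the protocol's statistical considerations, and that this row is the specific Part 2 definition of a symbol used in a stated formula. The intended reading can be inferred, but only by overriding the row.

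**Conclusion.** The contradiction is real and minor. Literal use of the Part 2 row overstates per-interval %fe by Cum %feu through the previous interval. That relation is exact, while the percentage-point ranges depend on the stated assumptions.

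The reach is limited. Aeu, Cum Aeu, Cum %feu, the fecal parameters, CLR and F do not depend on the faulty row. Combined urine and fecal recovery is not a stated Part 2 objective (protocol section 3, SAP section 5.2), and the PK analysis is descriptive only (SAP section 10.4.3). Correct interval values can be recovered as 100 (Aeu/dose) or as differences in Cum %feu.

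A reader might also infer that total recovery would be inflated past 100%, as in the 200 in the worked example. That would require Cum %fe to be built by summing the wrong %fe. The SAP wording does not require this. It equally allows the sum of interval percentages, which gives the correct 85.

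**What to change.** In the Part 2 urine table of SAP section 10.3.1, replace the %feu definition with the one already used in the SAP Part 1 table and in protocol section 7.3: "percentage of dose excreted in urine per sampling interval, where" %feu = 100 (Aeu/dose).

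Optionally, state Cum %fe = Cum %feu + Cum %fef, so that it cannot be built from a wrong interval term. This is a clarification and is not needed once the row is right.

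The cost is one corrected row and, if wanted, one added formula. Sampling, data collection and all other parameters stay as they are. Any Part 2 table shell or program that already uses %feu should be checked to confirm that it takes the interval value.
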